9. RESEARCH METHODS

9.1. Study Design

This non-interventional, voluntary PASS is designed as a single-center open-label survey.

Spontaneously reported safety data are available for pregnant MS patients treated with SC interferon beta therapy or an IM interferon beta therapy in the German PSP of the MSSC.

In addition, a prospective data collection is performed by completing a standardized questionnaire while interviewing MS patients who reported a “live birth” and for which a signed ICF is available.

9.1.1. Primary Endpoints

- Number and proportion of
 - live births without congenital anomalies,
 - live births with congenital anomalies,
 - ectopic pregnancies,
 - spontaneous abortions,
 - elective abortions,
 - preterm births,
 - stillbirths

A spontaneous abortion is defined as fetal death before 22 weeks of gestation. A still birth is defined as fetal death at > 22 weeks gestation. A preterm birth is a birth before 37 completed weeks of gestation.

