9.4. Data Sources

9.4.1. Retrospective Data Capture

Main data source for the retrospective data capture is the MSSC database, i.e. the entered pregnancy report (to be completed as soon as pregnancy becomes known) and pregnancy outcomes report (to be completed after completion of pregnancy).

The following data is extracted from the MSSC database:

- Demographic data (age, height, weight)
- SC Peginterferon beta-1a or IM Interferon beta-1a use, including treatment duration, prior to, during and after pregnancy
- Concomitant medication prior to and during pregnancy
- Pregnancy outcome (live birth without defect, live birth with defects, ectopic pregnancy, spontaneous abortion, elective termination of pregnancy, preterm birth, stillbirth), including gestation week and description of abnormalities of the fetus, reason for termination, diagnostics, etc.
- Complications during pregnancy

CONFIDENTIAL

The information contained herein may not be used, disclosed, or published without the written consent of Biogen MA Inc.

- Type of delivery (vaginal delivery: spontaneous, induced, instrumentally supported; Caesarean section: elective, medically indicated), complications during delivery or reasons for an intervention
- Placenta normal/abnormal
- Data on newborn (sex, weight, height, head circumference, Apgar 1 minute, Apgar 5 minutes, Apgar 10 minutes)

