9.5. Study Size

Since this is an exploratory study and no formal hypothesis-testing will be carried out, there is no formal sample size calculation. The sample size of this study depends on how many patients are eligible to participate in this observation and will agree to provide data for the questionnaire.

As of mid-July 2020, there were n = 202 pregnancy and pregnancy outcome reports for 184 female patients under SC Peginterferon beta-1a and n = 245 pregnancy and pregnancy outcome reports for 199 female patients treated with IM Interferon beta-1a in the MSSC database. The outcome of 368 pregnancies was a live birth, hence qualify for the prospective study part. About 290 patient questionnaires are expected to be completed during the telephone interview (80% return rate estimated). This number might increase until 15th October 2020 - the cut-off point for data collection.

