9.7. Data Analysis

This study is an observational study with focus on existing pregnancy reporting forms (retrospective part) and a patient's questionnaire which is completed at a single point of time (prospective part).

It will not be distinguished between the two treatments, i.e. the data will be pooled for analysis.

All documented data are analyzed by descriptive statistics, that is, no formal statistical hypothesis will be formulated, and no statistical tests will be carried out.

Categorical variables will be summarized descriptively by absolute frequencies and percentages. The denominator for all percentages will be the total number of pregnancies within the respective group, unless otherwise indicated. Percentages will be presented to one decimal place and will not be displayed for zero frequencies. A row denoted "Missing" will be included in all tabulations to clearly indicate the completeness of the collected data, i.e. missing data is included in the denominator of the percentages.

Continuous variables will be tabulated by descriptive statistics, i.e. the total number of pregnancies (n), number of pregnancies with missing values (Nmiss), mean, standard deviation, median, quartiles, minimum and maximum.

If sensible, free text entries will be transferred into appropriate encoding schemes to be analyzed in frequency tables. If appropriate, change of values during/after pregnancy to values before pregnancy will be calculated and analyzed using descriptive statistics or shift tables.

In case of missing or unknown data, no data imputation will be performed. For a complete presentation all obtained data will be listed.

A statistical analysis plan will be drafted and finalized before the end of the overall data collection to describe all analyses in more detail.

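### The only congenital-anomaly endpoint counts live births, so an anomaly recorded in a stillbirth, miscarriage or termination enters no endpoint

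*Protocol*

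**What the plan says.** Section 9.1.1 lists seven outcome categories as primary endpoints, each reported as a number and proportion. Two concern anomalies: live births without them and "live births with congenital anomalies". The loss categories have no anomaly split. Miscarriage and stillbirth are separated by gestational age alone ("A spontaneous abortion is defined as fetal death before 22 weeks of gestation"). Elective abortion is neither defined nor divided by reason.

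The outcome classes extracted from the service-center database have the same structure: "live birth without defect, live birth with defects, ectopic pregnancy, spontaneous abortion, elective termination of pregnancy, preterm birth, stillbirth" (section 9.4.1). Only live birth is divided by presence of a defect. The same item, however, also extracts detail, "including gestation week and description of abnormalities of the fetus, reason for termination, diagnostics, etc", which can hold an anomaly for a pregnancy that did not end in live birth.

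Section 9.7 sets the general analysis rules. On denominators: "The denominator for all percentages will be the total number of pregnancies within the respective group, unless otherwise indicated". On free text: "If sensible, free text entries will be transferred into appropriate encoding schemes to be analyzed in frequency tables". On everything else that was collected: "For a complete presentation all obtained data will be listed".

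Section 9.5 gives the counts as of mid-July 2020: 202 reports under SC peginterferon beta-1a, 245 under IM interferon beta-1a, and "The outcome of 368 pregnancies was a live birth".

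**The concern.** Whether a malformed fetus reaches live birth depends partly on prenatal diagnosis and on the severity of the defect. A termination after a prenatally diagnosed defect is counted in the same row as a termination for any other reason, and a malformed stillbirth is counted only as a stillbirth. A rise in such defects could then show as more elective abortions while the anomaly proportion stays the same.

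The primary objective (section 8.2) is the impact of exposure on pregnancy outcome. Section 7.1.2 cites 1.8% in the European registry against 2.1 to 4.1% in the general population for live births with anomalies, so readers will look to this row first for reassurance about malformations. The protocol's own definition of a serious adverse event (section 11.1.2) includes congenital anomaly without restricting it to live births, so the endpoint is narrower than the safety concept used elsewhere in the same document.

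**Working it through.** **Does another analysis recover these cases?**

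- Secondary endpoints (9.1.2): child abnormalities come from pediatric check-ups, and the analysis set requires a live birth (9.7.1.2). Not recovered.
- Subgroups (9.7.2): the same primary endpoint by treatment history. Not recovered.
- Further evaluation (9.7.3): names gestation week, type of birth and placenta among the items to tabulate, and lists complications. Fetal abnormality and reason for termination are not named.
- General rules (9.7): recorded abnormalities will be listed. Coding and tabulating free text is conditional.

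No named analysis counts anomalies across all outcomes.

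**Counts.** The inputs are from section 9.5. I take one report pair as one pregnancy.

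- The plan's own derived figure: 0.80 × 368 = 294.4, which agrees with the stated figure of about 290 questionnaires.
- Pregnancies: 202 + 245 = 447.
- Not live births: 447 − 368 = 79.
- Share that cannot enter the anomaly count: 79 / 447 = 17.7%.

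**Weight of one missed case.** Let a be anomalies in live births and k be recorded anomalies among the 79.

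- At the registry's 1.8%: a = 0.018 × 368 = 6.6. One further case adds 1 / 6.6 = 15%.
- At the upper population figure of 4.1%: a = 0.041 × 368 = 15.1. One further case adds 1 / 15.1 = 7%.

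**Range.** The protocol does not give k, so the values below are assumptions. The count a is rounded to a whole number, and the all-outcome proportion is (a + k) / 447.

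| k (assumed) | a = 7 | ratio to k = 0 | a = 15 | ratio to k = 0 |
|---|---|---|---|---|
| 0 | 1.6% | 1.00 | 3.4% | 1.00 |
| 1 | 1.8% | 1.14 | 3.6% | 1.07 |
| 2 | 2.0% | 1.29 | 3.8% | 1.13 |
| 4 | 2.5% | 1.57 | 4.3% | 1.27 |
| 8 | 3.4% | 2.14 | 5.1% | 1.53 |

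**Denominator, a separate matter.** Under the default rule in 9.7, seven anomalies would be shown as 7 / 447 = 1.6%. Per live birth they are 7 / 368 = 1.9%. The restriction of the numerator applies with either denominator, but the denominator has to be stated if the row is to be set beside the registry's.

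**The case against.** - **The information is not lost.** This stands. A reader might infer that anomalies in non-live outcomes disappear from the study. They do not: the fields are extracted, all data are listed, and pregnancy-related adverse events have already gone through routine pharmacovigilance (11.3.1). With 79 pregnancies a listing can be read case by case. But a listing is not a count, and none is specified.
- **A shift would still be visible.** This stands in part. Elective abortions, spontaneous abortions and stillbirths are primary endpoints, so a rise would appear in the same table. Without a split by anomaly, the row does not say whether malformations caused it.
- **The live-birth row matches its benchmark.** This stands. The registry and population figures in 7.1.2 are also for live births with anomalies, so the row should be kept. The protocol cites no benchmark for an all-outcome figure.
- **The SAP can handle it.** This stands for table layout: 9.7 defers detail to a SAP, which was not available here. It does not cover the endpoint itself, which 9.1.1 fixes as live births only.
- **Ascertainment in losses is poor.** This stands. Early losses are often not examined. The interview that fills gaps in the reports (9.4.2) is limited to live births (9.1; 9.2.1, criterion 7), so missing data for the other outcomes cannot be completed that way. This is a reason to label the combined figure, not to leave recorded cases out of it.
- **A few cases would change little.** This stands as a limit on the consequence. The study is descriptive and non-comparative. Seven anomalies in 368 live births has an exact 95% interval of 0.8% to 3.9%, and 11 / 447 = 2.5% lies inside it.

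**Conclusion.** The concern holds as a gap in the endpoint definition. As written, the study's only malformation proportion leaves out any anomaly recorded among 79 of 447 pregnancies (17.7%), and no other named analysis counts it.

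The proportion may therefore be understated, by an unknown amount. It is zero if no anomaly was recorded in the 79. Otherwise each case adds about 15% to an expected count of 6.6, assuming that the registry's 1.8% applies per live birth here. The counts are those of mid-July 2020 and may have grown by the cut-off.

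A reader might go further and conclude that a malformation signal is understated, or name a percentage of affected pregnancies missed. The protocol supports neither. It gives no anomaly count for the 79 and no breakdown of them by outcome, and some may be ectopic pregnancies or early losses in which an anomaly could hardly be assessed. The table above shows sensitivity to an assumption; it is not an estimate.

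The study remains usable. This is an inexpensive improvement to its main malformation figure.

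**What to change.** In section 9.1.1:

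1. Keep the live-birth anomaly figure for comparison with the registry, and state its denominator (live births, if it is to be read beside 7.1.2).
2. Add the number and proportion of pregnancies with a recorded congenital anomaly across live births, stillbirths, spontaneous abortions and elective terminations combined, with its own stated denominator.
3. Show elective terminations for fetal anomaly separately from those for other reasons, with a row for reason unknown.
4. Label the combined figure a minimum, because early losses are often not examined and gaps for non-live outcomes cannot be closed by the interview.

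The cost is protocol wording and a few table rows, with the abnormality and reason fields already extracted under 9.4.1 coded as a matter of course rather than at discretion. The downside is a figure with uneven ascertainment across outcomes and no benchmark in the protocol, so it should stand beside the live-birth figure and not replace it.

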9.2.1. Selection Criteria

The patients will only be included in the study if they meet all of the following criteria:

Inclusion Criteria

1. Female patients of at least 18 years at time of informed consent
2. Diagnosed RRMS or CIS (CIS indication only applicable for interferon beta-1a)

CONFIDENTIAL

The information contained herein may not be used, disclosed, or published without the written consent of
Biogen MA Inc.

3. Exposure to either SC Peginterferon beta-1a therapy or an IM Interferon beta-1a therapy before or during pregnancy
4. Registered in the PSP of the MSSC and agreed in writing to the privacy policy of the registration form
5. Reported pregnancy data (pregnancy report and pregnancy outcome report) available at MSSC. Note: only pregnancy data (i.e. obtained until 15 October 2021) will be considered.

For the prospective part of the study:

6. Ability to understand the purpose of the study and provide signed and dated study-specific informed consent form (ICF)
7. Pregnancy outcome in the retrospectively collected data was a live birth

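### The primary outcome definitions leave fetal death at 22 weeks unclassified, list preterm birth beside the outcomes it overlaps, and by default divide birth-based risks by all pregnancies

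*Protocol*

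**What the plan says.** Protocol Section 9.1.1 names seven primary endpoints, each to be given as a number and a proportion: live births without and with congenital anomalies, ectopic pregnancies, spontaneous abortions, elective abortions, preterm births and stillbirths. Three of them are defined.

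- For late fetal death the rule is: "A still birth is defined as fetal death at > 22 weeks gestation".
- For early fetal death the limit is set from the other side of the same week: "A spontaneous abortion is defined as fetal death before 22 weeks of gestation".
- The remaining definition concerns only the timing of delivery: "A preterm birth is a birth before 37 completed weeks of gestation".

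Section 9.4.1 describes the item extracted from the service-center database as "Pregnancy outcome (live birth without defect, live birth with defects, ectopic pregnancy, spontaneous abortion, elective termination of pregnancy, preterm birth, stillbirth), including gestation week".

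Section 9.7 sets the denominator: "The denominator for all percentages will be the total number of pregnancies within the respective group, unless otherwise indicated". It adds that "missing data is included in the denominator of the percentages". The protocol names no other denominator for the primary endpoints.

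For entry to the prospective part, criterion 7 in Section 9.2.1 requires: "Pregnancy outcome in the retrospectively collected data was a live birth".

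**The concern.** Three features of these rules affect the primary results.

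1. **Boundary.** One fetal-death category stops short of 22 weeks and the other begins after it. A death at 22 weeks has no category.
2. **Overlap.** Preterm birth describes when a birth happened, not how the pregnancy ended. Placing it in the same list as live birth and stillbirth leaves open whether a preterm live birth is counted once or twice, and in which row.
3. **Denominator.** Only a pregnancy that reaches birth can produce a preterm birth, and only a live birth can be a live birth with an anomaly. Dividing by all pregnancies, including ectopic pregnancies and abortions, gives a smaller figure than the risk per birth.

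Section 9.9 acknowledges that the study has no internal reference group, so readers will set its proportions against outside rates and need to know the basis. Section 9.7.2 also repeats the primary endpoint by exposure subgroup, each with its own pregnancies as denominator. Subgroups with different live-birth fractions would then show different anomaly and preterm percentages even at the same risk per birth.

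**Working it through.** **Inputs (Section 9.5, counts at mid-July 2020).** 202 pregnancies with outcome reports under SC peginterferon beta-1a; 245 under IM interferon beta-1a; 368 pregnancies ending in live birth; 80% expected questionnaire return.

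**The protocol's own figure.** 0.80 × 368 = 294.4, against a stated figure of about 290. It reproduces, so 368 is the base the protocol itself uses.

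**Boundary, as set logic on gestational age g.**
- Spontaneous abortion: g < 22.
- Stillbirth: g > 22.
- Neither: g = 22.

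If gestation week is stored as a whole number, which the protocol does not state, the uncovered band is the whole of 22+0 to 22+6. If days are stored, it is narrower. All fetal deaths lie among the 447 − 368 = 79 pregnancies without a live birth, which also include ectopic pregnancies and elective abortions.

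**Overlap.** The preterm definition covers any birth before 37 completed weeks and is not limited to live births. Each such birth is therefore also a live birth (with or without anomaly) or a stillbirth. Two codings are possible:
- One value per pregnancy: preterm live births leave the live-birth rows, and a preterm infant with an anomaly can leave the anomaly count.
- Several values per pregnancy: the seven rows can add to more than 100% of pregnancies.

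The protocol does not say which applies, nor whether the 368 live births include preterm ones.

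**Denominator.**
- Pregnancies: 202 + 245 = 447.
- Live-birth fraction: 368 / 447 = 0.823.
- Printed proportion = risk per live birth × 0.823, a relative reduction of 79 / 447 = 17.7%.

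| Risk per live birth | Cases among 368 | Printed per 447 pregnancies |
|---|---|---|
| Anomaly 1.8% | 6.6 | 1.5% |
| Anomaly 2.1% | 7.7 | 1.7% |
| Anomaly 4.1% | 15.1 | 3.4% |
| Preterm 5% (assumed) | 18.4 | 4.1% |
| Preterm 8% (assumed) | 29.4 | 6.6% |
| Preterm 10% (assumed) | 36.8 | 8.2% |

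The anomaly values are those cited in Section 7.1.2, taken here as per-live-birth risks; that section does not state their denominator. The protocol gives no preterm rate, so 5% to 10% is an assumption.

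**Stillbirths.** If the preterm risk is taken per birth, with an assumed 0 to 10 stillbirths added to the births, the factor runs from 368 / 447 = 0.823 to 378 / 447 = 0.846. If instead the comparison is with preterm live births per live birth, preterm stillbirths in the numerator offset the dilution. Full offset needs p × 79 of them: 0.05 × 79 = 3.95 up to 0.10 × 79 = 7.9, or about 4 to 8.

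**The case against.** Several counter-arguments stand, at least in part.

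- **The 22-week gap is a one-character slip.** It will touch few cases, and the source reports already carry an outcome label. This stands as to size. The definitions still disagree with full coverage.
- **Section 9.1.1 never says that the seven endpoints are exclusive.** This also stands: overlapping endpoints, each with its own count and proportion, are not in themselves an error. The difficulty lies in Section 9.4.1, which presents preterm birth as one value of a single outcome item and gives no rule for multiple values.
- **The denominator rule has an exception clause, and the analysis plan may use it.** True. The point is against the default that the protocol fixes. The clause does not repair the endpoint definitions.
- **A proportion per pregnancy is valid.** It is, and it is the natural basis for ectopic pregnancy and spontaneous abortion. It answers a different question from risk per birth. Because counts are reported and all data listed, a reader can recompute, provided preterm birth was not coded as an exclusive value.
- **The shift is small against sampling error.** With an assumed 7 anomalies, 1.9% of live births (exact 95% interval 0.8% to 3.9%) becomes 1.6% of pregnancies (0.6% to 3.2%). That is so, but the shift always goes one way for anomalies and disappears with a change of denominator.

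A reader might also infer that preterm infants will be lost from the child-development part, because their recorded outcome would not be a live birth under criterion 7. The documents do not show this. It follows only from single-value coding, which is nowhere stated; a preterm live birth is a live birth in ordinary meaning, and no selection rule excludes it.

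**Conclusion.** The point holds as a flaw in stated rules for the primary endpoints, moderate in size. Fetal death at 22 weeks is uncovered, probably with little numerical effect. The status of preterm birth in the outcome item is undefined, so the counts depend on an unstated coding choice. The default denominator prints anomaly risks at about 0.82 of their per-live-birth value. The same factor applies to preterm live births; for preterm births in general it is about 0.82 to 0.85 on a per-birth basis with 0 to 10 stillbirths, and could be offset against a per-live-birth figure.

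This rests on the mid-July 2020 counts, which may change by the cut-off; on reading the 368 as all live births, preterm included; and on the analysis plan not setting another denominator. A reader might conclude that the results will mislead against the rates in Section 7.1.2. That cannot be shown, because the denominator of those rates is not given.

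**What to change.** Change the wording in Sections 9.1.1, 9.2.1, 9.4.1 and 9.7 before data are extracted:

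1. Define stillbirth as fetal death at or after 22 completed weeks, so that it meets the spontaneous-abortion definition.
2. Report six mutually exclusive outcomes that, with any missing row, sum to all pregnancies: live birth without anomaly, live birth with anomaly, ectopic pregnancy, spontaneous abortion, elective abortion, stillbirth.
3. Derive preterm birth from gestation week as a separate yes/no attribute of births.
4. Use live births as the denominator for anomalies, and births (or live births, with a matching numerator) for preterm birth. Show these beside the per-pregnancy figures, overall and by subgroup.
5. State that preterm live births count as live births for criterion 7.

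The cost is text and a simple derivation: gestation week is already collected and no new data are needed. The stated anomaly and preterm proportions become somewhat higher, for anomalies by a factor of 447 / 368 = 1.21 at the current counts.

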9.1.2. Secondary Endpoints

- Average weight, average length, and average head circumference of the children from birth to 48 months
- Number and proportion of abnormalities diagnosed during pediatric check-ups under statutory programs in Germany and reported in the standardized German pediatric check-up booklet “Kinderuntersuchungsheft” (data on check-ups 1-8 will be collected covering the first 46 - 48 months of life). Refer to Annex 3 for recommended timepoints and details on the examinations.
- Number and proportion of women discontinuing SC Peginterferon beta-1a or IM Interferon beta-1a therapy during pregnancy and time to discontinuation in relation to beginning of pregnancy

CONFIDENTIAL

The information contained herein may not be used, disclosed, or published without the written consent of Biogen MA Inc.

- Number and proportion of women starting SC Peginterferon beta-1a or IM Interferon beta-1a therapy during pregnancy and time to start in relation to beginning of pregnancy
- Number and proportion of women restarting SC Peginterferon beta-1a or IM Interferon beta-1a therapy after birth and time to restart in relation to birth
- Number and proportion of women starting another MS therapy during/after pregnancy and time to start in relation to birth
- Number and proportion of women using other therapies during pregnancy (categorized by Paracetamol, other therapies for the alleviation of FLS), folic acid, medication for depression, corticosteroids, adrenocorticotrophic hormone, other therapies)
- Number and proportion of MS relapses in women with SC Peginterferon beta-1a or IM Interferon beta-1a therapy before, during and after pregnancy
- Change of EDSS during and after pregnancy to EDSS before pregnancy
- Lactation: number of women breastfeeding under SC Peginterferon beta-1a or IM Interferon beta-1a therapy and duration of SC Peginterferon beta-1a or IM Interferon beta-1a exposed breastfeeding
- Time to first MS relapse after introduction of the first supplemental feedings in women with SC Peginterferon beta-1a or IM Interferon beta-1a therapy during lactation

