8.3. Secondary Objectives

The secondary objectives of this study are applicable for a subpopulation of the above-mentioned population, i.e. for patients of whom data on a standardized questionnaire collected during a telephone interview is available. The secondary endpoints are as follows:

- To evaluate the impact of exposure to SC Peginterferon beta-1a or IM Interferon beta-1a before and during pregnancy on **child development** up to 48 months of age
- To assess the SC Peginterferon beta-1a or IM Interferon beta-1a **treatment behavior** for pregnant women or women becoming pregnant in daily real life
- To assess the other MS **treatment behavior** during/after pregnancy

CONFIDENTIAL

The information contained herein may not be used, disclosed, or published without the written consent of
Biogen MA Inc.

- To assess the use of certain concomitant medications (i.e. non-disease-modifying therapies) taken during pregnancy
- To evaluate the effect of SC Peginterferon beta-1a or IM Interferon beta-1a exposure before, during, and after pregnancy on MS **disease activity**
- To assess the effect of breastfeeding under SC Peginterferon beta-1a or IM Interferon beta-1a therapy on the MS disease activity
- To assess the benefit of exclusive breastfeeding versus complementary feeding on the MS disease activity in women breastfeeding under SC Peginterferon beta-1a or IM Interferon beta-1a therapy

CONFIDENTIAL

The information contained herein may not be used, disclosed, or published without the written consent of Biogen MA Inc.

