9.4.2. Prospective Data Capture

If the pregnancy report or the pregnancy outcome report is incomplete, i.e. the data above was not collected, the open questions will be addressed during a telephone interview performed by the MSSC and the new information will be entered into the MSSC database. No further assessments other than completion of the questionnaire are applicable for patients participating in the prospective study part. The patient questionnaire is completed at a single point of time during the telephone interview performed by the MSSC.

The patient questionnaire covers the following questions:

- Abnormalities diagnosed during pediatric check-ups under statutory programs as reported in the standardized German pediatric check-up booklet “Kinderuntersuchungsheft” (data on check-ups 1-8 will be collected covering the first 46-48 months of life)
- Pregnancy and family anamnesis
- Vitamin K prophylaxis
- Body weight, height, head circumference of the child as documented for check-ups 2-8.
- Lactation:
 - Exclusive breastfeeding and duration (1st week, 1 month, 2 months, 3 months, 5 months, 6 months, 7-9 months, 10-12 months, > 12 months) of breastfeeding
 - Supplemental feedings (starting month after birth)
- Other MS therapies (non-interferon beta-1a DMTs) during or after pregnancy and start relative to birth (during pregnancy, < 1 week after birth, after 1 week, after 2 weeks, after 3 weeks, after 4 weeks, after 6 weeks, after 2 months, after 3 months, after 4 months, after 5 months, after 6 months, after 7 months, after 8 months, after 9 months, after 10 months, after 1 months, after 12 months or later))
- Frequency of MS relapses in the year before pregnancy
- Time (1st trimester, 2nd trimester, 3rd trimester) and frequency of MS relapses during pregnancy

CONFIDENTIAL

The information contained herein may not be used, disclosed, or published without the written consent of Biogen MA Inc.

- Time (< 1st month, 1st – 2nd month, 3rd - 4th month, 5th - 6th month, 7th - 8th month, 9th - 10th month, 11th - 12th month, 13th - 14th month, 15th - 16th month, 17th - 18th month, > 18th months) and frequency of MS relapses after pregnancy/birth
- EDSS before, during and after pregnancy

The information collected by the MSSC will be stored in a secure database.

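### The exclusive-versus-complementary feeding objective has no matching endpoint, and relapse counts before, during and after pregnancy cover unequal windows

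*Protocol*

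**What the plan says.** One secondary objective in Protocol section 8.3 is "To assess the benefit of exclusive breastfeeding versus complementary feeding on the MS disease activity", restricted to women breastfeeding under one of the two interferons. The endpoint in section 9.1.2 that connects feeding with relapse is "Time to first MS relapse after introduction of the first supplemental feedings in women with SC Peginterferon beta-1a or IM Interferon beta-1a therapy during lactation". A separate lactation endpoint counts women who breastfeed on interferon and gives the duration, without reference to relapse.

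The general relapse endpoint is "Number and proportion of MS relapses in women with SC Peginterferon beta-1a or IM Interferon beta-1a therapy before, during and after pregnancy". EDSS has its own line: "Change of EDSS during and after pregnancy to EDSS before pregnancy".

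Section 9.4.2 fixes what is asked, once, by telephone:

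- relapses in the year before pregnancy;
- relapses by trimester;
- relapses after birth, in bands of up to two months to month 18 and then one open band;
- the month in which supplemental feeding began;
- breastfeeding duration, from the list "1st week, 1 month, 2 months, 3 months, 5 months, 6 months, 7-9 months, 10-12 months, > 12 months) of breastfeeding".

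Section 9.7 takes pregnancies in the group as the denominator of percentages unless otherwise indicated. It adds that "Continuous variables will be tabulated by descriptive statistics", meaning n, number missing, mean, SD, median, quartiles and range. The subgroups in section 9.7.2 are all by interferon history; none is by feeding practice.

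**The concern.** A contrast between two feeding states needs relapses and time at risk in both. An endpoint whose clock starts at the first supplemental feed observes only the second state. It would give a time-to-relapse figure with nothing to set beside it.

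The relapse endpoint is a count and a proportion over three periods of different length, the last of which depends on when each woman happens to be interviewed. Section 8.1 says the study will look for differences in disease progression by interferon exposure and breastfeeding practice, so these figures will be compared. Section 7 already cites evidence that relapses fall during pregnancy. A shorter pregnancy window would add an artefact in the same direction, and the two could not be told apart. It is also unclear whether the proportion counts relapses or pregnancies with at least one relapse.

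**Working it through.** **The plan's own figure.** The protocol gives no expected number of relapses. The nearest figure is the size of the analysis set: 368 live births × 0.80 = 294.4, which agrees with about 290 in section 9.5. (The Abstract's 310 would need 310/368 = 84.2%.)

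**Feeding objective against feeding endpoint.**

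| | During exclusive breastfeeding | After first supplemental feed |
|---|---|---|
| Needed for the 8.3 contrast | relapses and time at risk | relapses and time at risk |
| Covered by the 9.1.2 feeding endpoint | nothing, the clock has not started | time to first relapse |
| Collected under 9.4.2 | relapse bands from birth, breastfeeding duration | relapse bands, start month of supplements |

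Size of what is left out: with supplements from month 6 and a constant rate r, the share of women with a relapse before the clock starts is 1 − exp(−r × 6/12). For assumed rates of 0.2, 0.4 and 0.7 per year this is 9.5%, 18.1% and 29.5%.

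**Length of the three relapse windows.**

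- Before: 12 months (9.4.2).
- During: 40 weeks assumed, 40/52.18 × 12 = 9.2 months.
- After, shortest: pregnancy-data cut-off 15 October 2020 (Abstract and 9.5) to a first interview on 1 December 2020, 47 days / 30.4375 = 1.5 months.
- After, longest: 1 October 2014 (service start in 9.6, taken as the earliest birth) to 31 March 2021 (section 6), 2,373 days / 30.4375 = 78.0 months.

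The expected count is r × months/12, so with an unchanged rate the ratio of counts equals the ratio of window lengths, whatever r is:

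- during/before = 9.2/12 = 0.77;
- after/before = 1.5/12 = 0.13 to 78.0/12 = 6.5.

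The last two are extremes for single women. A woman interviewed at 38 months, near the middle of the range, gives 38/12 = 3.2.

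**Proportion with at least one relapse**, 1 − exp(−r × months/12):

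| r per year (assumed) | Before | During | After, 1.5 to 78 months |
|---|---|---|---|
| 0.2 | 18% | 14% | 3% to 73% |
| 0.4 | 33% | 26% | 5% to 93% |
| 0.7 | 50% | 42% | 9% to 99% |

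**Subgroups.** With follow-up spread evenly from a to b months and monthly rate q, the share with a relapse is 1 − [exp(−qa) − exp(−qb)] / [q(b − a)]. Take q = 0.4/12 in both groups:

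- a = 3.5, b = 24: 1 − (0.890 − 0.449)/0.683 = 36%;
- a = 24, b = 76: 1 − (0.449 − 0.079)/1.733 = 79%.

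The rate is the same, yet the proportions differ by a factor of about two. Dividing by person-time, or using a common window, restores a rate ratio of 1.0.

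**How much a fixed 18-month window would lose.** With births spread evenly from October 2014 to 15 October 2020 (72.5 months) and interviews on 1 February 2021 (3.6 months after the cut-off), (18 − 3.6)/72.5 = 20% of women have under 18 months after birth, and (12 − 3.6)/72.5 = 12% have under 12.

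**The case against.** Section 9.7 leaves detail to a SAP that is not shown, the study is descriptive, and section 9.9 already calls it non-comparative. The pregnancy denominator governs percentages only and can be overridden. The questionnaire fixes the year before pregnancy, splits pregnancy by trimester and bands the postpartum period, so a SAP could compute rates without contradicting the protocol. Much of this stands. It does not reach the feeding endpoint, whose starting point is fixed in 9.1.2: a SAP would have to replace that definition, not elaborate it. Nor does it change the fact that 9.1.2 names a number and a proportion, with no rate and no common postpartum window.

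Several stronger readings are tempting, and the text does not support them.

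- A reader might infer that women without a relapse or a restart by interview are dropped from the time summaries. Section 9.7 does not say so. It bars imputation of missing or unknown data, and a woman known to be event-free is neither. The method may be in the SAP. Medians and quartiles are planned as well as means.
- A reader might infer that nothing is recorded on relapse during exclusive breastfeeding. Section 9.4.2 collects postpartum relapses from the first month; what is missing is an endpoint that uses them for this contrast.
- A reader might infer that a 4-month breastfeeding duration cannot be recorded. The questionnaire itself is not shown, and the start month of supplements would often give the exclusive duration. It is a correction of detail.

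**Conclusion.** The point holds in two parts and one detail.

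1. The exclusive-versus-complementary objective has no matching endpoint, because the only endpoint tying feeding to relapse begins when exclusive breastfeeding is over, and no feeding subgroup fills the gap.
2. Relapse counts and proportions are defined over unequal windows, so they differ between periods, and can differ between subgroups, with no change in the relapse rate.
3. The duration list skips 4 months.

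The count ratios of 0.77 and 0.13 to 6.5 need no assumed relapse rate. They do rest on a 40-week pregnancy, a first interview on 1 December 2020, earliest births in October 2014 and the 15 October 2020 cut-off. Section 9.2.1 prints 15 October 2021 instead, which falls after the planned end of data collection and must be reconciled. The percentages rest on assumed rates of 0.2 to 0.7 per year.

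It does not follow that the disease-activity objectives are beyond answer. EDSS change is a separate endpoint, and the banded data would support a sound descriptive analysis if the endpoints asked for it.

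**What to change.** In section 9.1.2:

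- **Relapses.** Report relapses per person-year in fixed windows that match the questionnaire: the year before, each trimester, and postpartum months up to 6, 7-12 and 13-18, with person-time ending at interview. If a proportion is kept, say that it counts pregnancies with at least one relapse.
- **Feeding.** Replace or supplement the feeding endpoint with the relapse rate per person-month from birth, in women on interferon during lactation, by time-varying feeding status (exclusive, supplemented, stopped). Show it within postpartum bands, since exclusive feeding comes first and feeding status is therefore confounded with time since birth.
- **Times.** State that times to relapse, interferon restart and start of another therapy are censored at interview and summarised by Kaplan-Meier or life table. Both are descriptive and fit the no-testing design.

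In section 9.4.2, add 4 months to the duration list before interviews begin, and say whether the duration refers to exclusive or to any breastfeeding.

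The cost is wording and one questionnaire entry. The child's birth date and the interview date must be kept with each record; the lists in 9.4 do not name them, though the forms may hold them. One limit remains: with relapse bands of up to two months, the order of relapse and supplementation is unknown when both fall in the same band. An allocation rule has to be stated, and the contrast stays descriptive. The lactation count and duration endpoint and the EDSS endpoint need no change.
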